7.10 Safety Evaluation

Adverse events will be summarized by MedDRA System Organ Class (SOC) and High-level Term (HLT) at 30 days, 6 months, 1 year, and annually through 5 years. The number of events, number of subjects with event, and the Kaplan-Meier event rate (cumulative incidence) will be reported for each category and time point. Device related, procedure-related, and Serious Adverse Events (SAEs) will be reported similarly. A listing of adverse events will also be reported and will at minimum include the adverse event category, severity, treatment received, resolution, and investigator assessment of relationship to the device and procedure.

Additionally, listings of subject deaths, all device deficiencies, and device deficiencies which could have led to a serious adverse device effect will be reported.

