2 Years (between 730 to 760 days post implant)

- Clinical assessment, including NYHA classification
- TTE
- Medications
- KCCQ
- Adverse events and device deficiencies

3 Years (between 1095 to 1125 days post implant)

- Clinical assessment, including NYHA classification
- TTE
- Medications
- KCCQ
- Adverse events and device deficiencies

4 Years (between 1460 to 1490 days post implant)

- Clinical assessment, including NYHA classification
- TTE
- Medications

- KCCQ
- Adverse events and device deficiencies

5 Years (between 1825 to 1855 days post implant)

- Clinical assessment, including NYHA classification
- TTE
- Medications
- KCCQ
- Adverse events and device deficiencies

Other Evaluations

- Suspected stroke events should be confirmed by neurology consult and neuroimaging per site’s standard practice. A Modified Rankin Score assessment should be conducted at 1 and 3 months following any confirmed stroke event.
- The investigative team should follow their standard practices for assessment of suspected myocardial infarction, acute kidney injury, neurological events, prosthetic valve endocarditis, prosthetic valve thrombosis, etc.
- Non-protocol echocardiograms (e.g. performed for suspicion of prosthetic valve dysfunction) should be submitted to the ECL for evaluation.

Table 1. Summary of required evaluations and visit schedule

	Baseline	Implant	Discharge	30 Days	6 Months	Annual through 5 Years	1 month post stroke event	3 months post stroke event
Clinical assessment including NYHA	✓ ⁵		✓ ¹	✓	✓	✓		
Transthoracic Echo	✓		✓ ⁴	✓	✓	✓		
Multi-detector CT	✓							
12-lead ECG	✓		✓	✓	✓			
Coronary arteriography	✓							
Exercise Tolerance Test (unless contraindicated)	✓							
Cardiac MRI	✓				✓			
6-Minute Walk Test	✓				✓			
Spirometry	✓							
Complete Blood Count	✓							
Pro B-type natriuretic peptide	✓				✓			

Heart Team Assessment	✓							
Aortography		✓						
Hemodynamics		✓						
Medications	✓		✓	✓	✓	✓		
KCCQ	✓			✓	✓	✓		
EQ-5D	✓				✓			
Modified Rankin Score	✓						✓	✓
Adverse Events and/or device deficiencies ²	✓	✓	✓	✓	✓	✓		

Notes

1. NYHA not required at discharge
2. Adverse events should be assessed and captured at each follow-up visit after time of informed consent.
3. Discharge TTE used for “Device Success” should be performed > 12 hours and ≤ 7 days post implant
4. Clinical assessment and medical history required at baseline

Visit Windows

Baseline	Within 12 weeks prior to submission to ERC (except for MDCT and coronary arteriography)

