7.2 Evaluation and Documentation of Adverse Events and Device Deficiencies

Investigators are required to evaluate and document in the subject's medical records all adverse events (AE) and device deficiencies (per the definitions in Table 2) observed in study subjects from the time

they are enrolled until they are exited from the study. All AEs should be followed through their resolution.

All AEs that occur during the study need to be reported to Medtronic via the AE eCRF. Documented pre-existing conditions are not considered to be reportable unless there is a change in the nature or severity of the condition. Pre-existing events should be reported as AE in the situation where a new treatment has to be started or an existing treatment has to be changed to treat the adverse event and the event is accompanied with signs and symptoms. In addition, after the subject has completed his/her 6-month follow-up visit, only SAE, device-related AEs, and device deficiencies need to be reported to Medtronic.

Unavoidable events are conditions which do not fulfill the definition of an Adverse Event, meaning those medical occurrences, clinical signs (including toward abnormal laboratory findings), diseases or injuries that are not untoward in nature; specifically, those resulting from the intended injury such as the index TAVR procedure. The events listed in Table 3 are expected for patients undergoing TAVR, and do not need to be reported as AE, unless they occur outside of the stated timeframe, are otherwise considered to be an AE according to the treating investigator, or are suspected or confirmed to be device-related.

Table 3. Non-reportable medical occurrences associated with the index implant procedure

Event	Timeframe (hours) from the Index Procedure
Short transient episode of arrhythmia (including ventricular fibrillation) during index procedure	0
Confusion, anxiety and/or disorientation (other than TIA/stroke) starting within 48 hours with or without medical intervention	120 (5 days)
Temporary change in mental status (other than TIA/stroke) not requiring additional medical interventions or new medical assessments (e.g. CT)	72
Dizziness and/or lightheadedness with or without treatment	24
Headache with or without treatment	72
Sleep problems or insomnia with or without treatment	120 (5 days)
Mild dyspnea or cough with or without treatment	72
Oxygen supply after extubation/"forced breathing therapy"	48
Diarrhea with or without treatment	48

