11.1 Statement(s) of Compliance

The Evolut™ EXPAND TAVR I Feasibility Study will be conducted in compliance with the current version of the Declaration of Helsinki, the International Conference on Harmonization (ICH) Good Clinical Practice (GCP) R2 guidelines, the study protocol, the Sponsor's standard operating procedures and/or guidelines, and in accordance with federal, national and local laws, regulations, standards, and requirements of the countries/geographies where the study is being conducted.

These include but are not limited to the following:

- In the United States, the study will be conducted under a US FDA Investigational Device Exemption (IDE) in compliance with 21 CFR Parts 11, 50, 54, 56 and 812, and ISO 14155:2020 (except for Adverse Event reporting after 6-month visit as noted in section 7.2)
- In the EMEA region the study will be conducted in compliance with ISO 14155:2020 (except for Adverse Event reporting after 6-month visit as noted in section 7.2). The laws and regulations of the countries in which the study is conducted, included data protection laws, must be followed.
- In Canada, SOR/98-282, Section 79-88 will be followed. The study will be conducted in compliance with ISO 14155:2020 (except for Adverse Event reporting after 6-month visit as noted in section 7.2)
- In Australia, New Zealand the study will be conducted in compliance with local regulations and ISO 14155:2020 (except for Adverse Event reporting after 6-month visit as noted in section 7.2)

In addition, the study will be conducted in compliance with 21 CFR Part 11 and 54 in all participating geographies.

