
Probably related to the TAVR implant procedure
	
The relationship with TAVR implant procedure seems relevant and/or the event cannot be reasonably explained by another cause, but additional information may be obtained.

Causal relationship "Related" to the TAVR implant procedure
	
The event is associated with the TAVR implant procedure beyond reasonable doubt when:
 
 • the event is a known side effect of the TAVR implant procedure; • the event has a temporal relationship with the TAVR implant procedure; • the event involves a body-site or organ that 
 - the TAVR is applied to; - the TAVR implant procedure has an effect on; • the event follows a known response pattern to the TAVR implant procedure; • other possible causes (eg an underlying or concurrent illness/clinical condition or an effect of another device, drug, or treatment) have been adequately ruled out • harm to the subject is due to error in use 
In order to establish relatedness, not all the criteria listed above might be met at the same time.

Note:

Procedure related events refers to the procedure related to the initial application of the investigational medical device only and therefore not to any other procedures or treatments applied later throughout the clinical investigation, for instance to treat (serious) adverse events.

14. Version History

Version	Summary of changes	Justification of changes	Potential impact of the change on performance, effectiveness, or safety or other endpoints	Identification of the affected study documents	Author(s)/Title
Revision A	Not Applicable, New Document	Not Applicable, New Document	Not Applicable, New Document	Not Applicable, New Document	[name] Sr Clinical Program Mgr [name] Sr Clinical Research Specialist [name] Clinical Research Specialist [name] Sr Clinical Research Mgr [name] Associate Clinical Research Specialist
Revision B	Study name change to “Evolut™ EXPAND TAVR I Feasibility Study” (was previously Evolut™ System EXPAND I Feasibility Study). Administrative change only	N/A - Administrative Change only	N/A - Administrative Change only	Study name change to be updated in affected study documents, as applicable	[name] Sr Clinical Program Mgr [name] Sr Clinical Research Specialist [name] Clinical Research Specialist [name] Sr Clinical Research Mgr [name] Associate Clinical Research Specialist

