7.2 General Methodology

Continuous variables will be summarized descriptively with number of observations, mean, standard deviations, median, first and third quartiles, minimums and maximums. Categorical data will be presented as counts and percentages.

For time-to-event outcomes using Kaplan-Meier methods, the time points of 30 days, 6 months, 1 year, 2 years, 3 years, 4 years, and 5 years will correspond to 30, 183, 365, 730, 1095, 1460, and 1825 days post-implant, respectively. For each applicable time point, the event or event-free rate, the number of subjects at risk, the number of subjects with an event, the Greenwood standard error of the estimate, and the log-log transformed 95% confidence interval using the Greenwood standard error will be reported. For subjects with an event, the date of event will be based on the first event occurrence. For subjects without an event, date of censoring will be based on the latest of all follow-up visits, assessments, and events (for non-death events).

All statistical analyses will be performed using SAS version 9.4 or higher (SAS Institute, Cary, North Carolina, USA) or other widely accepted statistical or graphical software.

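### The 1- to 5-year all-adverse-event Kaplan-Meier rates in SAP 7.10 will be biased low, because most non-serious events need not be reported after the 6-month visit

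*SAP*

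**What the plan says.** SAP 7.10 (Safety Evaluation) plans summaries of adverse events by MedDRA System Organ Class "and High-level Term (HLT) at 30 days, 6 months, 1 year, and annually through 5 years". It gives event counts and subject counts, and states that "the Kaplan-Meier event rate (cumulative incidence) will be reported for each category and time point". The next sentence adds: "Device related, procedure-related, and Serious Adverse Events (SAEs) will be reported similarly". Since those three subsets come in addition, the first summary covers adverse events of every kind.

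Protocol 7.2 asks for all adverse events at first. Once a subject has completed the 6-month visit, however, "only SAE, device-related AEs, and device deficiencies need to be reported to Medtronic". Protocol 11.1 shows that this is intended: the statement of compliance with ISO 14155:2020 carries the qualifier "except for Adverse Event reporting after 6-month visit as noted in section 7.2".

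SAP 7.2 (General Methodology) fixes the risk set. For subjects without an event, "date of censoring will be based on the latest of all follow-up visits, assessments, and events".

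Two other protocol texts bear on the point. Note 2 to Table 1 in section 6.6 says: "Adverse events should be assessed and captured at each follow-up visit after time of informed consent". The note at the end of section 13.8.4 says: "Procedure related events refers to the procedure related to the initial application of the investigational medical device only".

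**The concern.** The late all-event tables would join two reporting regimes under one label: complete reporting up to the 6-month visit, and partial reporting afterwards. Take a subject who has a first non-serious, non-device-related event in year 2. If the site does not report it, the subject stays in the denominator as event-free until the last contact. The curve then flattens after 6 months partly because of the reporting rule, and a reader could take that for a real fall in incidence.

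Nothing planned would reveal this. SAP 7.4 relies on stating the number of subjects in each analysis, but these subjects appear fully observed. SAP 7.11 declares the SAP consistent with the protocol, and no SAP section mentions the change in reporting. One of the study's primary objectives is to estimate event rates for the design of pivotal studies.

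**Working it through.** **Which tables are exposed**

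| Planned summary | Still fully reportable after the 6-month visit? | Late rate |
|---|---|---|
| All adverse events, by class and term | No; only serious or device-related ones | Biased low wherever other events occur and go unreported |
| Procedure-related events | Partly; those neither serious nor device-related drop out | Biased low, probably by little |
| Serious adverse events | Yes | Unaffected |
| Device-related events | Yes | Unaffected |
| Any of these at 30 days or 6 months | Yes; the 6-month visit window is days 183 to 210 and the 6-month estimate is taken at day 183 | Unaffected if the visit is in window |

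The safety endpoints adjudicated by the Clinical Events Committee at 30 days and 6 months fall before the switch and are also unaffected.

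**Size (illustration)**

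The documents state no adverse event rates, so there is no figure of the plan to reproduce and every rate below is an assumption. Let h1 be the yearly hazard up to 6 months, h2 the hazard afterwards, s the share of late events still reportable (assumed 0.20 to 0.75) and T the time in years.

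- True rate = 1 − exp(−[0.5·h1 + h2·(T − 0.5)])
- Rate as planned = 1 − exp(−[0.5·h1 + s·h2·(T − 0.5)])

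*Constant hazard, h1 = h2 = 0.10*
- T = 1: true 1 − exp(−0.10) = 9.5%. As planned 1 − exp(−0.060) = 5.8% (s = 0.20) and 1 − exp(−0.0875) = 8.4% (s = 0.75).
- T = 5: true 1 − exp(−0.50) = 39.3%. As planned 1 − exp(−0.140) = 13.1% and 1 − exp(−0.3875) = 32.1%.

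*Front-loaded, h1 = 0.20, h2 = 0.05*
- T = 1: true 1 − exp(−0.125) = 11.8%. As planned 1 − exp(−0.105) = 10.0% and 1 − exp(−0.11875) = 11.2%.
- T = 5: true 1 − exp(−0.325) = 27.7%. As planned 1 − exp(−0.145) = 13.5% and 1 − exp(−0.26875) = 23.6%.

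*Procedure-related, 20% by 6 months and few late events*: rate at 5 years = 1 − 0.8·exp(−4.5·h2), with s·h2 in place of h2 for the planned rate.
- h2 = 0.002: true 20.7%, as planned 20.1% to 20.5%.
- h2 = 0.01: true 23.5%, as planned 20.7% to 22.7%.
- The gap runs from about 0.2 to 2.8 points.

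*Date of the switch.* If reporting narrows at day 210 instead of day 183 (constant 0.10), the planned rates become 6.4% and 8.55% at 1 year, and 13.6% and 32.3% at 5 years. The change is at most about 0.6 points.

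**Second formulation**

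Let a be the hazard of events that leave mandatory reporting and b the hazard of serious or device-related events. With no late capture of the first kind, the planned rate is 1 − exp(−[b·T + a·183/365]), against a true 1 − exp(−[(a + b)·T]). For a = 0.10 and b = 0.05:
- 1 year: 9.5% against 13.9%.
- 5 years: 25.9% against 52.8%.
- If sites volunteer half of the late events: 11.8% at 1 year and 40.8% at 5 years, still low.

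A Kaplan-Meier simulation of 75 subjects with a = 0.20, b = 0.10 and an assumed dropout hazard of 5% per year gave 18.1% against 25.9% at 1 year, and 45.3% against 77.9% at 5 years. In every scenario calculated from the formula, the day-183 rate did not change.

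**The case against.** **The rule is a reporting minimum.** Protocol 7.2 does not forbid other reports. Investigators must still document all events in the medical record, adverse events are listed at every annual visit, and Table 1 note 2 asks for capture throughout. The loss therefore depends on what sites do. This stands as a limit on the size of the bias, but it does not remove it. The note does not override the explicit exception in section 7.2. If some sites follow the note and others follow section 7.2, late rates also come to depend on site practice.

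**The illustrations may not resemble the actual tables.** Only the first event per subject counts. If 90% of subjects had some event by 6 months (an assumption), the overall any-event rate could be at most 10 points too low. For a single uncommon term at an assumed 1% per year, the 5-year rate would be 1.4% to 3.8% against 4.9%, or about 1 to 3 subjects instead of 3.7 in 75. The 20% to 75% share has no source in the documents. It could be higher if events classed as possibly related count as device-related, which the protocol does not settle. All of this is fair: the direction is certain and the size is not.

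**The main long-term results are safe.** Mortality is not affected, bioprosthetic valve dysfunction comes from core laboratory data, and hospitalisations and heart failure events should largely remain reportable as serious. The exposed tables are supplementary and descriptive. That limits the consequence, but the tables would still be wrong as labelled.

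**A 6-month visit held before day 183**, out of window, would end full reporting early for that subject. This small qualification to the 6-month rates also stands.

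**Conclusion.** The concern holds. SAP 7.10 plans all-event rates to 5 years from data that the protocol stops requiring in full after the 6-month visit, and the censoring rule in SAP 7.2 turns unreported events into event-free follow-up. The bias is downward. It disappears only if all late events are serious or device-related, if sites report the rest anyway, or if no others occur.

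Under the assumed constant 10% per year, the 5-year shortfall is about 7 to 26 points (39.3% against 32.1% and 13.1%), and the 1-year shortfall about 1 to 4 points. It is smaller for uncommon terms and probably small for procedure-related events, which are tied to the initial implant and partly remain reportable. This should be corrected before the late tables are produced. It does not touch the key endpoints.

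**What to change.** In SAP 7.10:

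1. Limit the all-event and procedure-related tables and Kaplan-Meier rates to 30 days and 6 months (day 183).
2. At 1 to 5 years, report only serious adverse events, including serious procedure-related ones, and device-related adverse events.
3. Add a footnote to those tables and to the adverse event listing, for example: *From the 6-month visit onward, sites were required to report only serious or device-related events and device deficiencies (CIP 7.2).*

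A footnote alone would disclose the problem but leave rates that cannot be interpreted. Censoring the all-event analysis at the 6-month visit leaves nobody at risk at 1 year or later, so it comes to the same restriction.

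The cost is SAP wording and the loss of a few supplementary late tables. No data collection changes and no protocol amendment is needed.

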7.11 Changes to Planned Analysis

This analysis plan is consistent with the CIP for which the plan was developed. Any deviations from the planned analysis in the CIP will be documented in an amended statistical analysis plan, when possible, and/or will be described with justification and rationale in the study report.

8. Validation Requirements

Level 1 validation (independent validation) will be used for the analysis datasets and for all safety and efficacy endpoints. Level 2 validation (peer review), at minimum, will be used for additional analyses, data summaries, and listings.

9. References

